## Addiction and Behavior Related to Menthol Cigarette Substitutes

*craving reduction, improved mood with use, and ease of use [on daily diaries, will report the greatest substitution of study product for UBMC.]*

### B. Significance

**Menthol cigarette prevalence is increasing:** In the face of historic declines in the prevalence of cigarette smoking in the U.S., the proportion of menthol cigarette users increased significantly from 35% in 2008-2010 to 39% in 2012-2014. Significant increases in menthol cigarette prevalence occurred in all age groups, with youth (12-17 years old) and young adult (18-24 years old) smokers reporting the highest prevalence of menthol use among smokers (53.9% and 50.0%, respectively). These findings were echoed by data from the 2013-2014 Population Assessment of Tobacco and Health (PATH) Study, with 60% of youth and 47% of young adult smokers using mentholated cigarettes. These changes are consistent with growth in menthol cigarette market share and menthol cigarette prevalence can only be expected to increase in youth and young adults given recent expansions in the distribution of menthol cigarettes by the largest U.S. cigarette companies.

**Role of menthol in smoking initiation and maintenance:** Reviews of tobacco industry documents underscore the relationship between menthol cigarette use, youth smoking initiation and tobacco dependence, as understood and manipulated by the tobacco industry. The appeal of menthol flavoring has been demonstrated to influence intention to smoke and initial smoking, with youth more likely to experiment with menthol cigarettes than older age groups. Additionally, young smokers who start with menthol cigarettes are more likely to increase or maintain their smoking behavior over time. There are several mechanisms by which menthol in cigarettes has demonstrated to influence the initiation and maintenance of smoking, as indicated by tobacco industry documents as well as independent research: 1) menthol's cooling and analgesic properties mask the harshness and taste of cigarette smoke, making it more appealing; 2) menthol's refreshing sensory qualities increase the positive, or rewarding, properties associated with smoking; 3) menthol inhibits nicotine metabolism, causing the smoker greater systemic exposure to nicotine; and 4) menthol may change smokers' puff topography causing them to take more puffs. These mechanisms, long known by the tobacco industry, allowed them to engineer a nicotine delivery device that would not only attract new smokers but also make it more difficult for established smokers to quit.

**Menthol cigarettes, public health, and threats to the efficacy of a ban on menthol cigarettes:** The 2009 Family Smoking Prevention and Tobacco Control Act banned certain characterizing flavors in cigarettes and their components (i.e., tobacco, filter, and paper). The law did not include menthol, nor did it address flavors in non-cigarette tobacco products. However, the Act makes clear that the Food and Drug Administration (FDA) has the authority to issue a product standard to ban menthol in cigarettes, or any other tobacco product, to protect public health. Reviews of the scientific evidence by the FDA and its Tobacco Product Scientific Advisory Committee led to a report concluding that it is "likely that menthol cigarettes pose a public health risk above that seen with non-menthol cigarettes" and "removal of menthol cigarettes from the marketplace would benefit public health in the United States." FDA has continued to request information on the potential effects of a ban on menthol in cigarettes, including in the July 2017 announcement of its comprehensive approach to tobacco and nicotine regulation. The 2009 ban on flavored cigarettes provides a key example of the potential intended and unintended consequences of such a ban. A recent study using data from the 1999-2013 National Youth Tobacco Surveys showed that the flavored cigarette ban was associated with reductions in the prevalence of past 30-day cigarette smoking and number of cigarettes smoked in youth, as intended. However, youth prevalence of past 30-day flavored cigar, pipe, and menthol cigarette use increased following the 2009 ban, suggesting substitution of other flavored tobacco products for flavored cigarettes. This is consistent with evidence of tobacco companies exploiting loopholes in tobacco regulation to maintain sales of their flavored products. Djarum, for example, launched clove

## Addiction and Behavior Related to Menthol Cigarette Substitutes

filtered cigars in the U.S. in anticipation of the 2009 ban on flavored cigarettes and sales of their clove filtered cigars increased by more than 1400% between 2009 and 2012. **Thus, while manufactured flavored cigarettes are no longer available, the public health benefit of this product standard was attenuated by the presence of accessible commercially-available substitutes in the marketplace.**

Recent trend data highlight growth in U.S. sales of mentholated products, including filtered cigars from 2011 to 2015. Population data show significant correlation between cigar use and menthol cigarette use. These patterns of co-use may be related to the pervasiveness of characterizing flavors, including menthol, in these products. [*Studies on effects of a hypothetical ban on menthol in cigarettes among menthol smokers support behavioral intentions to switch to another tobacco product or to non-menthol cigarettes.*] **Importantly, these data suggest that polyuse of menthol tobacco products is already occurring, possibly enabling future substitution of other tobacco products for menthol cigarettes in response to an FDA ban. [They also highlight non-menthol cigarettes as a possible substitute under such a ban.]**

**Implications:** Data on recent changes in the tobacco marketplace and population patterns of tobacco use in youth and adults underscore the potential substitution of other tobacco products for menthol cigarettes in the context of a ban. The increased use of cigars and pipe tobacco in youth following the 2009 ban on flavored cigarettes is particularly important given that flavored filtered cigars are often indistinguishable from cigarettes and [*flavored pipe tobacco is used to make roll-your-own cigarettes.*] Mentholated pipe tobacco (for RYO cigarettes), menthol filtered cigars, [*and non-menthol cigarettes*] appear to be plausible substitutes for menthol cigarettes. The goal of the current study is to examine the abuse liability and substitutability of these potential menthol cigarette substitutes in the laboratory and in an extended observation period. Findings from this study will provide key information on the potential unintended consequences of a ban on menthol in cigarettes (i.e., the extent to which these substitutes would appeal to and be used by existing menthol cigarette smokers). They may also inform how FDA treats other non-cigarette tobacco products used as menthol cigarette substitutes in future proposed rulemaking, [*for example, extending the ban to menthol filtered little cigars or menthol pipe tobacco.*] **The scientific premise of this study is that examining abuse liability and substitutability of menthol cigarette substitutes will inform estimates of the public health impact of a ban on menthol in cigarettes. This information is required for FDA's regulatory impact analysis to pursue such a ban. This study will also provide a model for future research on the potential public health impact of flavor bans in non-cigarette products, noted as another priority by FDA in their plan for comprehensive nicotine regulation.**

## Innovation

This study is poised to contribute to FDA's decision-making on menthol and to advance the field of tobacco regulatory science in a number of ways. It will be the first to estimate the substitutability of combusted menthol cigarette substitutes in adult smokers, which could attenuate the health benefit of a public health standard banning menthol in cigarettes. Previous studies have examined the addiction potential of cigarettes, including menthol cigarettes, but have not compared measures of abuse liability and substitutability across menthol cigarettes and likely menthol cigarette substitutes. This information is needed to determine how the availability of other menthol products may affect the public health impact of a ban on menthol in cigarettes [*and whether additional product standards would be needed (e.g., ban on menthol in filtered little cigars, pipe tobacco) to maximize the public health benefit of such a regulation.*] Second, this study pairs standardized measures of abuse liability, use patterns, and subjective effects in the lab with *ad libitum* outpatient use of the study product to approximate "real-world" use. Daily diaries will begin to elucidate real-time mechanisms associated with substitution. Finally, the high prevalence of menthol cigarette use in youth and young adults and recent data on the flavored cigarette ban suggest that a ban on menthol cigarettes may drive alternative product use in young smokers. [*Stratified sampling of young adults*

[figure not shown]
## Addiction and Behavior Related to Menthol Cigarette Substitutes

(aged 21-24) and adults aged 25+ will ensure adequate sample size to explore whether age influences the uptake of menthol cigarette substitutes by young adult vs. older adult menthol smokers.]

### C. Approach and Preliminary Studies

Our team brings combined expertise in all areas necessary for the successful implementation of a clinical/clinical laboratory study examining the substitutability of other combusted mentholated non-cigarette tobacco products for menthol cigarettes. Specifically, our team has strong expertise conducting survey and longitudinal cohort research examining the 1) the role of menthol in smoking initiation, dependence, and cessation, 2) the impact of a menthol ban on population health including the substitutability of non-menthol and menthol cigarettes, and 3) the use of flavored and non-cigarette tobacco products among youth, young adults, adults. We have also conducted five clinical/human laboratory studies examining the pharmacological, toxicological, and physiological effects of non-cigarette tobacco products including two ongoing studies examining the impact of flavors and sweeteners on waterpipe tobacco smoking (R03DA041928; R03DA041928-02S1). In each of these studies, we assessed the abuse liability, topography, nicotine delivery, toxicant exposure, and use behaviors of the non-cigarette tobacco product under investigation. All of these methods are very familiar to our team and we have experienced great success utilizing them. Our team has also conducted several short-term as well as long-term randomized trials assessing tobacco use behavior. Lastly, our team has significant experience to collect daily diary data to examine tobacco use and behavioral correlates among smokers. These studies have resulted in excellent retention (>80%) with high-rates of daily diary completion (80-88%).

**Theoretical Framework:** The proposed study is guided generally by behavioral economic theory as well as an established framework for abuse liability assessment used by the FDA to assess drug products, including tobacco. Specifically, abuse liability assessment involves determining the likelihood that use of a product will lead to persistent and problematic use through a series of specific tests across multiple domains (**Figure 1**) including: 1) self-administration tasks, to determine a product's rate of self-administration over time; 2) forced choice tasks, to determine if one product is preferred over another; 3) hypothetical purchase tasks, to determine how much of a product is consumed at different prices or changes in consumption relative to changes in the price of a different product; and 4) positive and negative subjective effects, to determine the psychoactive effects of a drug; and 5) suppression of withdrawal/craving with product use, to determine whether a product can prevent the effects of abstinence in nicotine dependent individuals. Products with a higher abuse liability will be self-administered at a relatively higher rate, preferred over the other product when forced to choose, less sensitive to higher costs to obtain it, greater positive effects/fewer side effects, and more effectively suppress craving and withdrawal symptoms. The proposed study will examine each of these domains.]

Addiction and Behavior Related to Menthol Cigarette Substitutes

## D. Research Design and Methods

### 1. Design Overview

**Figure 2** depicts the sequence of the proposed study. Using an in-laboratory and *ad libitum* outpatient mixed design, 135 current menthol cigarette smokers will complete a three phase, 3-week study. Over the 3-week study time period, participants will attend 5

**Figure 2. Study Overview**

in-person lab visits. At the beginning of each visit, pregnancy tests will be completed to ensure that the participant is not pregnant. During visit 1, participants will complete a PROP taste test to measure a participants' perceived intensity to taste. In *Phase 1*, utilizing a randomized crossover design, participants will complete [4 smoking sessions,] each session smoking a different product examining each [participants' puff topography while sampling the product, the product's ability to suppress nicotine craving/withdrawal, and the product's demand indices. Products will include participants' usual brand menthol cigarette (UBMC) as well as 3 commercially-available alternatives, including an mFLC, a pre-assembled mRYO product (menthol tobacco + menthol tube), and an nmC.] All sessions will occur following 12-hrs of nicotine abstinence and be separated by 48-hrs. Participants will complete daily diaries for one-week during this period to more accurately assess current use of their UBMC. In *Phase 2*, participants will [select their preferred study product from Phase 1] and be instructed to completely substitute the product for their UBMC for one week. Participants will complete daily diaries during this period to more accurately assess degree of substitution and perceived effects in real-time. In *Phase 3*, participants will complete a final in-lab visit to assess the substitutability of their preferred product, under simulated ban conditions using a progressive ratio task. In all phases, multiple domains of abuse liability will be assessed, including product administration (in-lab puff topography and daily diary self-report measures), product liking and craving and withdrawal suppression (in-lab and daily diary self-report), and hypothetical purchase tasks to simulate demand.

### Study Weaknesses and Design Considerations

What if none of the study products substitute for menthol cigarettes? Industry evidence has shown menthol cigarette smokers prefer their own brand among other menthol brands. Therefore, it is possible that our study products will not be sufficiently satisfying to substitute for UBMCs. [To address this, we have included a Newport non-menthol cigarette as one of the substitutes in Phase 1 and allow participants to choose their preferred study product for the extended observation period in Phase 2. To reduce the likelihood of a null finding, we include multiple measures of substitution, including use behavior via daily diary (Phase 2) and a progressive ratio (PR) task comparing the study product to the UBMC in Phase 3.] The PR task is a sensitive measure to assess changes in substitutability of the study product. Lack of significant findings, however, will also be informative to FDA in determining whether or how other non-cigarette products should be included under a proposed ban on menthol in cigarettes.

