**Aim 2: To assess the substitutability of menthol cigarette alternatives.** [*H2a: A significantly higher portion of product preference selections for Phase 2 will favor nmC than all other alternatives. H2b: Participants' use of study products will significantly increase over the one-week substitution period. H2c: Under simulated UBMC ban conditions, >80% of participants will substitute at least 50% of their UBMC use with study product.]*

**Aim 3: To evaluate which product characteristics and perceived effects influence greater substitution.** *H3: Participants reporting higher product satisfaction, including "throat hit", menthol-specific sensory effects,*

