### Recruitment Feasibility and Retention

**Recruitment:** We intend to recruit 135 current menthol cigarette smokers (and assume 20% attrition) over a 16-month period (4 months of study preparation, 16 months of recruitment, and 4 months of data cleaning/analysis and manuscript prep). Therefore, we need ~6 participants to be recruited and complete study procedures each month to achieve our goal; we are confident that our recruitment approaches will yield sufficient numbers given our successful history of recruitment for other tobacco-related research of similar design. Menthol cigarette smokers will be recruited from advertisements through a variety of media outlets and the internet, including Study Search, as well as community events. Participants from other studies who have agreed to be contacted regarding other study opportunities will also be contacted. Staff from those studies will prepare contact letters/emails and call participants on behalf of this study. Participants interested will be referred to this study for screening. Participants will access the screening questionnaire using a public survey link generated by REDCap. Based on our team's previous studies we conservatively assume a 20% attrition rate; thus, we will need to recruit 135 participants to have 80 complete the study. Menthol smokers will be screened over the telephone. Participants who meet the following eligibility criteria will be asked to take part in the study.

**Inclusion Criteria:** 1) a current menthol cigarette smoker (>90% menthol cigarette use;  $\geq 5$  cigarettes per day) for at least the past 6 months, 2) between 21-24 (young adult or 25-50 years old (aged 25+), 3) willing to provide informed consent and abstain from all tobacco and nicotine use for at least 12 hours prior to the five lab sessions, 4) willing to complete two weeks of daily dairies, 5) read and speak English, and 6) have access to a smart phone or email

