## E. Statistical Methods

### 1. Power Analysis

Since our main goal is to evaluate the substitutability of menthol alternatives in the context of a menthol cigarette ban, statistical power is based on differences in abuse liability measures (Hypothesis 1a) and product substitution (Hypothesis 2c). Sample size estimates relied on means and standard deviations of data collected as part of a University of Vermont laboratory study examining the abuse liability of cigarettes containing different doses of nicotine. A sample size of 80 subjects has 81% power to detect decreases in product satisfaction of up to 50% compared to their usual brand (mean for UBMC 5.5, SD 1.3). In addition, a sample size of 80 participants has greater than 80% power to detect decreases of 68%–72% in the cigarette purchase task indices of maximum expenditure, maximum price and price sensitivity, similar to what we found in our laboratory study. This sample size also provides 81% power to estimate 80% use of the preferred alternate product more than half the time during Phase 2 with a 95% confidence interval of 66%–94%.

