### 2. Data Analytic Plan

Statistical analyses will be performed using SAS 9.4 and an alpha of .05. Background measures will be summarized by product (UBMC, mFLC, mRYO, nmC), as appropriate. Continuous variables will be presented as mean  $\pm$  SD; categorical variables will be presented as counts and proportions. We will apply a transformation to normalize the distribution and stabilize the variance of the residuals where appropriate.

Hypotheses 1a and 1c: We will use Repeated Measures Analysis of Variance with Tukey-adjustment to examine differences between the alternatives and the UBMC in abuse liability assessed at each product lab session. Assuming statistically significant product differences, this post-hoc test will allow us to not only compare each product to the UBMC, but will also allow comparison of the alternative products with each other. Because product introduction in Phase 1 will be randomized using a Latin Square, a fixed effect for session and a random effect for sequence will be included in all analyses.

Hypothesis 2a: Product preference will be examined using a Chi-Square Test, comparing the proportions of participants choosing each alternate product for further use.

Hypothesis 2b: We will examine the trajectory of use behavior outcomes using Linear Mixed Model (LMM) regression analysis. We will employ a random intercept or slope parameter, as appropriate, and model the covariance structure for the repeated outcome measures, while accounting for potential confounders, including gender and baseline cigarettes/day.

Hypothesis 2c: This aim will be analyzed as a Chi-Square Test of Goodness of Fit to test the proportion of use compared to 80%.

Hypothesis 3: We will examine whether differences in product characteristics and changes in perceived effects collected via daily diary are associated with increased substitution of the alternate product over the seven-day period using generalized LMM regression analysis, similar to that outlined in H2b.

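### A non-significant H2c result cannot be read as failure to substitute: with 80 completers it means that 71% to 89% of participants were observed to substitute

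*Combined protocol and SAP*

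**What the plan says.** Under Study Weaknesses and Design Considerations (Section D.1), the plan raises the possibility that none of the products substitutes for the usual brand menthol cigarette (UBMC). It describes two safeguards: a non-menthol cigarette is among the alternatives, and substitution is measured in several ways ("To reduce the likelihood of a null finding, we include multiple measures of substitution"). It then says: "Lack of significant findings, however, will also be informative to FDA in determining whether or how other non-cigarette products should be included". The sentence refers to a menthol ban and names no hypothesis.

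The hypothesis on the level of substitution is H2c in Section A: "Under simulated UBMC ban conditions, >80% of participants will substitute at least 50% of their UBMC use with study product". Section E.2 sets its test: "This aim will be analyzed as a Chi-Square Test of Goodness of Fit to test the proportion of use compared to 80" per cent. On the significance level, E.2 says "Statistical analyses will be performed using SAS 9.4 and an alpha of .05", without stating sidedness. The planned number of completers is 80 ("thus, we will need to recruit 135 participants to have 80 complete the study"), and E.1 uses the same number.

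Section D.3 gives cut-offs for single measures. A cross-price elasticity above 0.2 means substitution, below -0.2 complementarity, and between them independence. A diary ratio of study product to UBMC above 1 means substitution at least half the time. No section says how a non-significant test is to be interpreted, or what confidence bound would support a conclusion of low substitution.

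**The concern.** The D.1 sentence answers the question of what follows if nothing substitutes, so a reader will naturally connect a lack of significance with a lack of substitution. For H2c that connection fails. The null value is 80%, not zero or some low share, so a non-significant result places the observed share near 80%.

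The other Aim 2 tests do not fill the gap, because neither has no substitution as its null. A null H2a means that the three alternatives were chosen about equally. A null H2b means that use did not rise over the week, which would also happen if participants switched fully on the first day, as instructed.

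The study is meant to detect unintended substitution under a menthol ban. If a non-significant H2c were reported as bearing on whether to leave products out of a ban, data showing high substitution could be used for the opposite conclusion.

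**Working it through.** **Inputs.** Completers n = 80 (recruitment section and E.1). Null proportion p0 = 0.80 (H2c in Section A; E.2). Alpha 0.05 (E.2). The chi-square goodness-of-fit test is two-sided by construction. Each participant counts as substituting at least 50% or not.

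**The plan's own figure.** E.1 gives 81% power and a 95% confidence interval of 66% to 94% around 80%, for n = 80. The interval does not reproduce:
- Wald: 0.80 ± 1.96 × √(0.80 × 0.20 / 80) = 0.80 ± 0.088, or 71.2% to 88.8%.
- Wilson: 70.0% to 87.3%. Exact: 69.6% to 88.1%.
- A half-width of 14 points needs n = 1.96² × 0.16 / 0.14² ≈ 31.

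The 81% does reproduce as the exact power of the two-sided test against 80% when the true share is 66% (80.8%). The printed range therefore looks like a detectable difference labelled as an interval. It is a planning figure, not a rule for reading a null.

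**Non-significant range, n = 80.** The expected count is 64, and the statistic is (x − 64)²/64 + (x − 64)²/16 = (x − 64)²/12.8, compared with 3.841.
- x = 57 or 71: 49/12.8 = 3.83, p = 0.0504, not significant.
- x = 56 or 72: 64/12.8 = 5.00, p = 0.025, significant.

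So 57 to 71 of 80 (71.25% to 88.75%) is non-significant. The continuity-corrected and exact binomial tests give the same range.

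**What the lowest null count shows.** 57 of 80 has an exact 95% interval of 60.0% to 80.8%. Every non-significant count therefore excludes a minority of substituters.

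**Chance of each result by true share (exact binomial, n = 80).**

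| True share | Significant below 80% | Not significant | Significant above 80% |
|---|---|---|---|
| 50% | >99.9% | <0.1% | 0% |
| 60% | 97.5% | 2.5% | 0% |
| 71% | 46% | 54% | 0% |
| 80% | 2.2% | 96.5% | 1.3% |
| 85% | <0.1% | 87% | 13% |
| 88% | 0% | 63% | 37% |
| 90% | 0% | 41% | 59% |

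**Sensitivity to the number of completers.** The plan also says "we conservatively assume a 20% attrition rate", and 135 × 0.80 = 108, not 80. With n = 108 the statistic is (x − 86.4)²/17.28, and the non-significant range is 79 to 94 of 108 (73% to 87%).

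**Sensitivity to sidedness.** With a one-sided test for more than 80% at n = 80, any count below 70 (normal approximation) or 71 (exact) is non-significant. The range then has no lower limit, and a null would not separate low from high substitution at all.

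**The case against.** The strongest reply is that the D.1 sentence is general. It names no test, follows a reference to several measures, and says only that null findings will be informative about whether or how products are included. It does not say that a null means no substitution or that a ban need not cover a product. A reader might infer that the plan proposes this conclusion; the documents do not support that. Also, in the scenario D.1 raises, the planned two-sided H2c test would be significant, not null: at a true share of 60% or lower it rejects downward in more than 97% of trials. Both points stand. They limit the concern to a missing rule of interpretation, and they also show that a null H2c is not the signature of failed substitution.

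A reader might also infer that the plan sets no substitution level anywhere and learns nothing about individual products. That goes too far. D.3 fixes cut-offs, including a cross-price elasticity for each product, H2a examines choice by product, and the Phase 1 comparisons set each product against the UBMC and against the others. None of these is affected. What D.3 and E.2 lack is a confidence bound or decision rule linking the cut-offs to a null result.

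Finally, 71% to 89% is a range of observed shares. It would be wrong to infer that any true share in that range reliably gives a null: at a true 71% or 89%, non-significance is close to a coin toss (54% and 52%).

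**Conclusion.** The point holds for H2c and is a matter of interpretation. It calls for no change of test, endpoint or sample size. A non-significant result with 80 completers means an observed share of 71% to 89% (73% to 87% with 108), which is majority substitution. When H2c is true, the chance of missing it is 87% at a true 85%, 63% at 88% and 41% at 90%.

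This rests on the two-sided chi-square test as written, and on one yes/no outcome per participant. The documents do not fully settle that outcome: H2c is worded for simulated ban conditions, E.1 refers to Phase 2 use, and E.2 speaks of the proportion of use.

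H2c pools whichever product each participant preferred, and H2a predicts that this will most often be the non-menthol cigarette. Its null is therefore not specific to the non-cigarette products named in D.1. Miss rates for each product cannot be given, because the documents state no split of choices and plan no test against 80% by product.

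Misreporting to the regulator is a risk that the wording leaves open, not something the plan sets out to do.

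**What to change.** Replace the D.1 sentence, and add to H2c in E.2, text such as: *A non-significant result will not be interpreted as absence of substitution. The proportion of participants substituting at least 50% will be reported with an exact 95% confidence interval, and conclusions about low substitution will be based on the upper confidence limit against a proportion fixed before analysis.* The sponsor chooses that proportion.

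Report the proportion by chosen product descriptively, with exact intervals, next to the share of participants choosing each product (H2a) and its cross-price elasticity. Set no decision rule by product. Those who chose a product are self-selected and may be few: even 0 substituters among 5 choosers has an exact upper limit of 52%.

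In the same edit, state the sidedness of the H2c test, settle its outcome, and correct or relabel the 66% to 94% interval in E.1.

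The cost is a few sentences in D.1, E.1 and E.2, with no new data. The one downside is that some results will have to be reported as inconclusive.
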